2. ADEQUACY OF PROTECTION AGAINST RISKS

a. Recruitment and Informed Consent

Subjects will be recruited in collaboration with two stroke clinics: (1) the Ralph H. Johnson VAMC Physical Medicine and Rehabilitation (PM&R) stroke services and (2) the Medical University of South Carolina (MUSC) Comprehensive Stroke Center. Recruitment and Informed Consent: The PI ([name]) and Co-I ([name]) are both fully funded VA researchers. They have a collaborative relationship with the Ralph H. Johnson VAMC PM&R Service for patient recruitment. In addition they are both appointed in the Department of Health Sciences and Rehabilitation Research at MUSC. They have a strong collaborative relationship with the MUSC Stroke Center. The Department of Health Science and Research recruitment coordinator will be informed of the inclusion criteria for the present proposal.

The recruitment coordinator will interface with the VAMC and MUSC for recruitment. If potential participants are identified that meet inclusion criteria the PI or Co-I will contact participants by phone to determine if they want to participate in the current study. If they wish to participate they will be scheduled for a time for the PI to obtain informed consent for the study proposed.

Consent will be obtained by the PI after reviewing the protocol and consent form with each potential subject. If a potential subject is deemed unable to participate in informed consent, consent will be obtained from a relative with the patient present. For patients consenting themselves, every attempt will be made to have a relative present during the informed consent. The MUSC IRB will approve the informed consent form, and the Ralph H. Johnson VAMC R&D committee will also approve the protocol.

b. Protection against Risk

Potential discomforts or risks for participation in this study are minimal. Each participant will be asked to perform a series of upper extremity movements that may include reaching, grasping and lifting a series of common everyday objects. Participants may be seated or standing for these activities. While standing, all participants will be closely guarded by study personnel to monitor and maintain balance.

There may be a temporary skin reaction to the adhesive used to secure the motion analysis markers or EMG sensors to the skin. To minimize this, the skin will be cleaned before and after the markers or sensors are placed on the skin and hypoallergenic electrode gel and tape will be used on the skin. A skin reaction is a rare occurrence and resolves within 1-2 days. All participants will be asked if they have had any previous experience of allergic reaction to specific gel or tape types. If the participant has a history of reaction to gels/tapes then the limb will be wrapped in non-sticky pre-wrap and motion sensors will be attached to it. Pre-wrap is a soft wrap often used under casts or braces.

During rehabilitation treatment, participants will be asked to practice using the arm most affected by stroke. They will perform 200 movement repetitions during rehabilitation treatment. The will include reaching, grasping and lifting common everyday objects. Participants may be seated or standing for these activities. While standing, all participants will be closely guarded by study personnel to monitor and maintain balance. In previous studies, 200 repetitions of reaching movement using the hemiparetic UE required approximately 2 hours with no reports of increased pain or fatigue although subjects will be offered a rest break after every set of 10 movements.

A licensed occupational or physical therapist will oversee all evaluation and treatment sessions. The therapist will monitor the participant for safety and offer rest breaks when he/she determines that the patient needs one.

Participants will undergo screening before the MRI. The screening form has been uploaded. This screening form asks questions such as "do you have any metal in your body?", "are you claustrophobic?" If the participant answers "yes" to any of these screening questions, we will not obtain the MRI. While in the MRI scanner, the participant will be given an emergency ball to squeeze at any time that he/she is feeling discomfort and desire to be pulled out of the scanner. The participant can stop the scanning protocol at any time. All participants will wear earplugs to protect against possible hearing damage. A member of the research team will accompany the participants to the scanner and remain outside the MRI but will remain in voice contact with the subject while he/she is in the scanner (via a microphone). The research team member will provide reassurance, answer questions and coach the subject as needed. If subject is pregnant, they will not be enrolled in this substudy.

All data and documents associated with this study will be coded with a unique study identifier and securely stored in either a password protected dedicated computer network drive or a locked cabinet in the secured office of the Principal Investigator. The master list linking the study identifiers to the individuals and any PHI will be stored separately from the study data and kept in a password protected file on the MUSC secure network (MUSC patients) or VA network (VA patients).

3. POTENTIAL BENEFITS OF THE PROPOSED RESEARCH TO THE SUBJECTS AND OTHERS

Subjects are hypothesized to benefit from the short intervention. Benefits could include more "normalized" reaching and muscle activity patterns in the arm most affected by stroke. However, because rehabilitation interventions are sometimes not effective, it is possible that there will be no long term benefits. The findings in this study may assist therapists in decision-making to optimize post-stroke rehabilitative therapy and enhance beneficial outcomes for persons with neurological injury and upper extremity impairment. The results of this study will be used to develop or refine rehabilitation treatments to promote more recovery of function. In addition, the study will provide critical information about how best to match a rehabilitation therapy to a patient given his/her specific upper extremity impairments. Our ultimate aim is to generate a scientific-based model for rehabilitation of post-stroke upper extremity motor impairment that is effective and efficient in accomplishing patient goals for arm and hand use.

4. IMPORTANCE OF THE KNOWLEDGE TO BE GAINED

The present proposal seeks to systematically investigate the effects of an UE therapy strategy that is designed according to clinical and laboratory-based measurements of post-stroke UE motor function. This Merit Review award, if funded, will enable a more comprehensive understanding of how to link the measurement of specific

motor processes that are impaired with injury to interventions targeted at these motor processes. It will also permit a greater understanding of how intervention affects specific motor processes.

The risks to the subjects are minimal because the rehabilitation testing and programs are similar to those provided to persons with stroke in inpatient and outpatient rehabilitation settings. The PI and study coordinator are both licensed occupational therapists with extensive experience providing rehabilitation programs to persons with stroke. There are no drugs, devices or biologicals in this study. This study is comprised only of post-stroke rehabilitation aimed at improving arm movement through task-practice.

5. SUBJECT SAFETY AND MINIMIZING RISKS (Data and Safety Monitoring Plan)

Any adverse events will be recorded and monitored as required by our Institutional Review Board. On-campus medical services will be available in the event of adverse events to the subjects. Subjects will be able to terminate the movement analysis and/or task-practice protocol at their request at any time without prejudice. All documents with PHI (e.g., the ICF) will be stored in locked cabinets in the PI's office in the MUSC College of Health Professions Research Building which is also a VA designated research space.

All electronic files containing PHI will be stored on the VA network (VA patients) or MUSC network (MUSC patients) in password protected files which will be encrypted at the highest level of encryption available at the time of data storage.

A licensed occupational or physical therapist will oversee all evaluation and treatment sessions. The therapist will monitor the participant for safety and offer rest breaks when he/she determines that the patient needs one.

F. REFERENCES/LITERATURE CITATIONS

1. American-Heart-Association. *Heart Disease and Stroke Statistics — 2010 Update*. Dallas, Texas: American Heart Association.

The Ralph H. Johnson VA Medical Center and the MUSC are located in close proximity to one another on a shared campus with a majority of the staff having dual appointments (VA+MUSC). For example, the PI has an appointment as Assistant Professor in the Department of Health Sciences and Research in the MUSC College of Health Professions. There is a close, open working relationship between the local VA Medical Center's PENTAD and ACOS for Research and counterparts at MUSC. This is especially evident within MUSC's Strom Thurmond Biomedical Research Institute Building, half of which is leased by the VA to support VA ORD's bench research and animal research activities. The distinction between MUSC and VA faculty is almost non-existent with investigators working side-by-side in an atmosphere that promotes intellectual sharing of scientific knowledge and expertise that has led to the development of new collaborations between VA and MUSC investigators. This has allowed VA and MUSC investigators to propose and carryout a large number of innovative and intriguing investigations. Several of these collaborations have resulted in the discovery and use of new methodology not readily considered for use in a particular area of investigation that has added a whole new dimension to many of our investigators' protocols. The VA Research Office provides excellent administrative support to investigators in

all areas. Of significant note is the level of support they provide in the preparation of applications in response to VA initiatives. They take the lead in coordinating and preparing all non-scientific aspects, including biosketches/other support forms, budgets and justifications, letters of support, intramural reviews, etc. which allows investigators to focus all their energies on the scientific aspects of the application. MUSC is a research intensive university, with an academic medical center, and is the state's largest medical complex and the only tertiary/quaternary care referral center in the state. In FY 2009, MUSC faculty received grants and contracts totaling more than \$217 million, with funding from NIH totaling \$103.3 million. The College of Health Professions was ranked #9 in the country in total funding for similar colleges; the Department of Neurosciences, an integrated department of clinical and research neuroscientists that contains several nationally renowned senior investigators in stroke-research, ranks # 5 in the nation in NIH funding. MUSC is home to the JCAHO-certified SC Comprehensive Stroke and Cerebrovascular program, MUSC Stroke Center of Excellence and the REACH Stroke Network. The Stroke Center directed by [name]. conducts innovative clinical trials throughout the state as well as through national networks, and offers remote urgent consultations through a new Web-based system that allows virtual examination of patients and CAT scans at community medical centers across the state.

Center for Biomedical Imaging (CBI): The CBI provides state-of-the-art imaging resources to support clinical and research activities, provide opportunities to advance the imaging field, disseminate new technologies and approaches to the larger community, and train and mentor young investigators interested in developing and applying biomedical imaging to clinical and research problems. The CBI includes approximately 4500 square feet of space at [name], as well as approximately 9000 square feet in the new Bioengineering Building. This proposal will utilize the brain imaging and stimulation facilities available at the [name] location of the CBI. The [name] location is the main facility for human imaging research and houses a Siemens 3T TIM Trio MRI scanner equipped with integrated fMRI paradigm presentation equipment. It is located directly across the street from the main hospital and is 1 block from the Institute of Psychiatry. The scanner operates with a 100% mandate for research use and is covered by a master research agreement with Siemens Medical. The site also contains an image analysis laboratory, a brain stimulation laboratory, and bioengineering facility along with subject interview and changing rooms. Research access is coordinated and billed through CBI and a web-based signup system. Researchers also have access to clinical Siemens 1.5T and 3T Verio MR scanners, located within the Radiology Department in the Clinical Sciences Building.

Laboratory

Upper Extremity Motor Function Laboratory: The Upper Extremity Motor Function Laboratory is a 900 square foot VA/MUSC laboratory located with the College of Health Professions Research Building ([name]) on the campus of Medical University of South Carolina. This laboratory is designated as VA space through a formal Memorandum of Understanding between MUSC and the VA. The laboratory is located in the same building as the offices of the PI, Co-I, engineer and research therapy staff. It features equipment capable of collecting kinematic, kinetic, electromyographic, strength, and metabolic data. The motion analysis laboratory is adjacent to a small workshop available for the construction, repair, and alteration of simple mechanical devices. This space is located in close proximity to the VA Medical Center (within 2 blocks). The laboratory is a shared resource of the college and is supported in part by the Department of Health Sciences and Research, of which the Co-PI is Chairman. The College enthusiastically supports the integration of VA research within its research portfolio.

Clinical

One avenue for recruitment of hemiparetic subjects for this project is the MUSC JCAHO-certified Stroke Center is directed by [name]. The Stroke Center at MUSC includes highly trained neuroscience nurses, a neuroscience service line administrator, stroke neurologists, neurointensivists, interventional neuroradiologists, diagnostic neuroradiologists, cerebrovascular neurosurgeons, medical intensivists, neurosonology technologists, dedicated neurosciences critical care pharmacists, comprehensive rehabilitation services, dedicated case managers and social workers, and a hospital-based ground transport system. The program holds Joint Commission's Certificate of Distinction for Primary Stroke Centers which recognizes centers that make exceptional efforts to foster better outcomes for stroke care. The MUSC Stroke Center sees over 50 new stroke patients per month and routinely screens all patients for eligibility to research studies. Their database currently contains information on several hundred persons who have given consent to be contacted for stroke research studies. The Stroke Center research team will assist with recruitment by reviewing the patient rosters to identify potential participants. Potential participants will be given information while inpatient and again when they are seen

for follow up in the outpatient clinic. The Stroke Center research team will establish communication with the potential participants and act as a liaison with the PI to facilitate recruitment. In addition to facilitating subject recruitment, these facilities offer the PI opportunities to gain exposure to clinical problems by attending grand rounds, observing inpatient rehabilitation, and interacting with clinicians.

In addition, investigators within the Department of Health Sciences and Research have established collaboration with [name]., Chief of Neurology at VAMC Charleston. In the last 5 year period, over 3500 veterans with stroke were seen throughout the Charleston Veterans Affairs catchment area along the South Carolina and Georgia coast. The Charleston VAMC conducts 4 neurology follow-up clinics per week in which Veterans with stroke are seen.

Computer

All staff have personal computers in their office that are linked together on a network. All office computers are equipped with necessary software for professional productivity (e.g., Microsoft Office, Internet Explorer, Adobe Acrobat, Matlab, etc.). The office computers are all on automated backup systems and linked for file sharing. Laboratory computers are also on the network, so that data are readily available to investigators. The PI has software available for conducting (a) item response theory data analyses (Winsteps Rasch Analysis, Rasch Unidimensional Modeling, Multilog Item Response Theory Modeling); (b) mathematical data analysis (Matlab) and (c) statistical data analysis (SPSS, SAS).

Office

Project investigators and staff have dedicated offices, telephones, and up-to-date office technology software. The PI and Co-I have offices in the College of Health Professions Research Building (with an approved VA off-site waiver). Project staff will have office space in the building. Conference telephones and videoconferencing capabilities are readily available. Well-appointed conference rooms with teleconferencing capabilities are readily available on a scheduled basis for conference calls and collaborator meetings. Support staff and standard office services are available to facilitate the project.

I. INVESTIGATOR BROCHURE

No Investigator Brochure

J. APPENDIX

Patient-Targeted Upper Extremity Rehabilitation After Stroke – Recruitment Questionnaire

Patient-Targeted Upper Extremity Rehabilitation After Stroke – Recruitment Questionnaire

Inclusion criteria:

1. Experienced an ischemic stroke at least 3 months prior
2. Passive range of motion in affected shoulder, elbow, and wrist within functional limits
3. 20-80 years of age

Exclusion criteria:

1. Pain in the affected upper extremity that would interfere with movement
2. Unable to understand 3-step directions
3. Unable to attend the study-related treatment or evaluation sessions
4. Orthopedic condition in back, UE, or impaired corrected vision that would alter kinematics of reaching.

1. Date of stroke_____
2. Medical records and MRI or CT available for review before participation yes no
3. Adult age 20 – 80? Current age_____
4. Gender: Male Female
5. Affected side: left right
6. Do you have passive ROM
 - a. Shoulder yes no
Motions_____
Limitations_____
Pain with PROM yes no scale: 1 2 3 4 5 6 7 8 9 10
Does your pain interfere with movement: yes no
 - b. Elbow yes no
Motions_____
Limitations_____
Pain with PROM yes no scale: 1 2 3 4 5 6 7 8 9 10
Does your pain interfere with movement: yes no
 - c. Wrist yes no
Motions_____
Limitations_____
Pain with PROM yes no scale: 1 2 3 4 5 6 7 8 9 10
Does your pain interfere with movement: yes no

7. Able to understand 3-step directions: yes no

Ex: 1. Place your right hand on the table.
 2. Tap your index (pointer) finger 3 times on the table.
 3. Make a fist with your right hand.

8. Total study time will be 8 weeks. All participants, in all groups will engage in 4 evaluations, 9 rehabilitation sessions and 1 follow-up session which will be 30 days after the last rehabilitation therapy session. The first session will take approximately 3-4 hours and all other sessions will take approximately 3 hours.

Are you willing and available to participate in all sessions and follow-up yes no

9. Do you have orthopedic back conditions that prevent you from:

a. Sitting up for prolonged periods without trunk support yes no
 b. Sitting on a chair/stool without back support yes no

c. Do you have pain during or after sitting unsupported on a chair yes no

Pain scale: 1 2 3 4 5 6 7 8 9 10

Does your pain interfere with movement yes no

d. Do you wear splints, slings, or other supportive devices on your hands or wrist yes no

e. Do you wear an eye patch yes no

f. Do you have impaired corrected vision that would alter your ability to reach or grasp objects? yes no

Notes: _____

Questionnaire was conducted:	Phone	With Individual	Caregiver	Both
	In person	With individual	Caregiver	Both

 Recruiter

 Date of Questionnaire

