**Medical University of South Carolina
Protocol**

PI Name: [name], OTR/L

Study Title: Patient-Targeted Upper Extremity Rehabilitation After Stroke

Version 4.0

Date: 08/01/2016

TABLE OF CONTENTS

Specific Aims	p.1
Background and Significance	p.2
Preliminary Studies	p.7
Research Design and Methods	p.12
Protection of Human Subjects	p.20
References/Literature Citations	p.25
Consultants	p.28
Facilities Available	p.29
Investigator Brochure	p.30
Appendix	p.30

A. SPECIFIC AIMS

Exciting advances in rehabilitation research have increased knowledge about the potential for upper extremity (UE) motor recovery after stroke. Experimental models provide strong evidence that intensive task practice which is made progressively more and more challenging drives cortical reorganization. We restructured the Fugl-Meyer UE Assessment (FMA-UE) to reflect a progression of UE motor recovery typically seen in individuals with stroke. This novel restructuring (1) allows the identification of unique categories of UE motor impairment that can be the target for specific treatment, and (2) maps increasingly more difficult movement tasks for task-practice sessions. The restructured FMA-UE is the first comprehensive framework with which to link measurement of patient-specific UE motor ability to personalized treatment.

The Specific Aims of this VA funded (VA Merit Award, #I01RX000799, [name] PI) project are to:

Aim #1: Compare the effects of targeted rehabilitation to non-targeted rehabilitation on UE motor function.

Hypothesis: Targeted intervention will result in a greater pre- to post-intervention reduction of UE motor impairment when compared to non-targeted intervention. **Approach:** This is a prospective double-blind RCT with parallel arm design. 130 individuals with mild, moderate, and severe post-stroke UE hemiparesis will be enrolled. Subjects within each impairment level will be randomly assigned to either a targeted or non-targeted treatment group for 2 hr rehabilitation sessions 3x/week for 4 weeks (a total of 12 sessions). Targeted practice is defined as a treatment targeted at specific UE motor deficits characterizing each UE impairment level enabled by our original measurement method. Non-targeted practice is a standard of care treatment that consists of task practice with no guidance from measurement to choose appropriate tasks or address specific underlying deficits.

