Dose: All subjects in all groups will engage in 12 rehabilitation sessions (3x/week over 4 weeks).. Recent data suggest that the dose of practice, e.g., number of movement repetitions, is important to produce neural reorganization and motor learning.⁷¹ We therefore will provide approximately 200 reach-to-grasp/touch repetitions per session which previous research has shown to be safe for people with stroke and feasible to accomplish in 2-

3 hours.⁷² **Treatment Groups:** Targeted practice is defined as an evidence-based intervention targeted to specific UE motor deficits characteristic of persons in each UE impairment level. Non-targeted task practice is defined as a “standard of care” intervention that consists of task practice with no guidance from measurement to choose appropriate tasks to address specific underlying deficits. **Table 4** presents a summary of the treatments.

Table 4: Summary of treatments

Rasch FMA-UE Impairment Level	Rasch FMA-UE Person Measure	Targeted Treatment	Non-Targeted Treatment
Mild	>2.44 logits	Forced-use task practice	Functional Upper Extremity Training
Moderate	- 0.22 to 2.44 logits	Task practice with trunk restraint	
Severe	<-0.22 logits	Task practice with trunk restraint and faded arm support	

Targeted Practice Treatment: A person with mild UE motor impairment has a 50% probability of accomplishing FMA-UE items requiring fine motor coordination and dexterity, i.e., items well-matched to his/her ability described in Table1. For people with this level of UE motor impairment *Forced use task practice* is an optimal evidence-based intervention.⁷³ Forced use therapy, like Constraint-Induced Movement Therapy²⁸ although not delivered in its “signature” dose, restrains participants’ less affected UE in a glove to prevent its use thereby “forcing” exclusive use of the affected UE. The premise of the strategy is that repetitive object grasp, manipulation reduces “learned non-use”.⁷⁴ The intervention is shown to improve fine motor dexterity, movement speed, and smoothness.^{31,32}

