Potential discomforts or risks for participation in this study are minimal. This is a prospective study with parallel arm design. Subjects will undergo 4 evaluation sessions (Pre-treatment, Mid-Treatment, Post-Treatment, 30 day Follow Up). Assessments will consist of (1) clinical rating scale assessments and (2) motion and EMG analysis. During both types of assessment sessions, subjects will be seated comfortably. They will be asked to perform UE movements commonly performed in everyday life (e.g., lift arm to eye level while keeping elbow straight, pick up a soda can). Sensors for motion and EMG analysis are attached to the participants' skin. There may be a temporary skin reaction to the adhesive used to secure the motion analysis markers or EMG sensors to the skin. To minimize this, the skin will be cleaned before and after the markers or sensors are placed on the skin and hypoallergenic gel and tape will be used on the skin. A skin reaction is a rare occurrence and resolves within 1-2 days. All participants will be asked if they have had any previous experience of allergic reaction to specific gel or tape types. If they answer yes, then we will avoid placing markers or sensors directly on the skin. Instead we will wrap the limb in non-sticky "pre-wrap" and attach motion sensors to it. Pre-wrap is a soft wrap often used under casts or braces.

Subjects will be randomized to two stroke rehabilitation treatment groups; "targeted" vs. "non-targeted" and will engage in 12 rehabilitation treatment sessions. The only difference between the treatments is that the "targeted" group will receive specific instructions from the therapist regarding the participants' quality of movement during rehabilitation treatment (e.g., straighten elbow, sit tall). During rehabilitation treatment, participants will be asked to practice using the arm most affected by stroke. They will perform 200 movement repetitions during rehabilitation treatment. The will include reaching, grasping and lifting common everyday objects. Participants may be seated or standing for these activities. While standing, all participants will be closely guarded by study personnel to monitor and maintain balance. In previous studies, 200 repetitions of reaching movement using the hemiparetic UE required approximately 2 hours with no reports of increased pain or fatigue although subjects will be offered a rest break after every set of 10 movements.

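### The recruitment questionnaire screens availability for 9 rehabilitation sessions where the protocol delivers 12, and the protocol contradicts itself on whether a 30-day follow-up evaluation takes place

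*Protocol*

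**What the plan says.** **Sessions.** Specific Aims (Aim 1, Approach) sets "2 hr rehabilitation sessions 3x/week for 4 weeks (a total of 12 sessions". The Dose paragraph in Research Design and Methods says "All subjects in all groups will engage in 12 rehabilitation sessions (3x/week over 4 weeks". Potential Risks, in Protection of Human Subjects, says participants "will engage in 12 rehabilitation treatment sessions". Item 8 of the Recruitment Questionnaire differs: "All participants, in all groups will engage in 4 evaluations, 9 rehabilitation sessions and 1 follow-up session which will be 30 days after" the last therapy session. It adds "Total study time will be 8 weeks" and asks "Are you willing and available to participate in all sessions and follow-up". The form lists as an exclusion "Unable to attend the study-related treatment or evaluation sessions". The same exclusion stands in the Protection of Human Subjects criteria, though not in the Methods list.

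**Evaluations.** Potential Risks says "Subjects will undergo 4 evaluation sessions (Pre-treatment, Mid-Treatment, Post-Treatment, 30 day Follow Up", each made up of rating scales plus motion and EMG analysis. The Evaluation Sessions paragraph in Methods gives a total of three full evaluations (pre, mid, post), with extra FMA-UE administrations at the end of weeks 1 and 3. The neuromechanical procedure gives three time points for kinematics and EMG. The Project Timeline has a Year 4 entry for completing follow-up tests, with no time point or measure.

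**Analyses.** Aims 1 and 2 use pre-to-post change. Aim 3 uses five FMA-UE occasions ending at post-intervention. The SAP's Time factor is Pre, Mid, Post. Its Missing Data paragraph describes each patient as observed for three weeks.

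**The concern.** Item 8 is working text. A recruiter reads it out, and the yes/no answer feeds an attendance exclusion. If its session count is wrong, availability is tested against a schedule the trial does not run, and a candidate may agree to fewer sessions than will be asked of them.

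The evaluation count raises a different problem. Staff following the Methods text would stop at the post-treatment evaluation, while staff following Potential Risks would bring people back at 30 days. If the visit takes place, participants give time to a measurement with no stated use. Any later analysis of whether a difference persists would then be chosen after the data are in hand.

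**Working it through.** **1. Which session count is right?** Sessions = sessions per week × weeks.
- Protocol: 3 × 4 = 12. This reproduces the figure in Specific Aims and Dose; Potential Risks gives the same total.
- Form: 9. At 3 per week that is 9 / 3 = 3 weeks.
- Difference: 12 − 9 = 3 sessions, and 3/12 = 25%.

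The assessment plan supports 12. Evaluation Sessions and Aim 3 (Observed Variables) treat the end of week 3 and post-intervention as separate FMA-UE occasions. In a 3-week course they would coincide unless the post evaluation were delayed.

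**2. Is the form's total time also wrong?** The follow-up runs from the last session. Count days from the first session and assume Monday/Wednesday/Friday spacing (the plan names no weekdays).
- 12 sessions: last session at 3 × 7 + 4 = 25 days; follow-up at 25 + 30 = 55 days. With the last session on the final day of week 4: 27 + 30 = 57 days.
- 9 sessions: last session at 2 × 7 + 4 = 18 days; follow-up at 18 + 30 = 48 days. With the last session on the final day of week 3: 20 + 30 = 50 days.
- Form: 8 × 7 = 56 days.

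The stated total fits the 12-session course with no lead time added. The 9-session course reaches about 8 weeks only with something like the one-week pre-test interval of the pilot (Background, section 2h): 48 + 7 = 55 days. The present plan gives no such interval.

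**3. Evaluation counts side by side.**

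| Place | Evaluations | 30-day visit |
|---|---|---|
| Methods, Evaluation Sessions | 3 | not listed |
| Methods, neuromechanical procedure | 3 time points | not listed |
| Project Timeline | no count | follow-up tests, undated |
| Potential Risks | 4 | included in the 4 |
| Questionnaire item 8 | 4 plus 1 follow-up | in addition to the 4 |

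Read literally, the counts are 3, 4 and 5.

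**4. Does any analysis use the visit?** Aim 1: pre to post. Aim 2: pre to post. Aim 3: five occasions, the last at post. SAP Time factor: three levels, the last at Post. TMS: five time points, the last at post-treatment. None uses a 30-day measurement.

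**5. Does the SAP's 3-week phrase change anything?** Treatment lasts 4 weeks, so the phrase is too short with or without follow-up. The missing-data rules carry no time limit and Post is a named Time level, so no analysis changes.

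**The case against.** The strongest reply is that little follows from this. The form is a pre-screen, and under Recruitment and Informed Consent the investigator reviews the protocol and consent form with each person before consent. The total duration told to candidates is about right. A secondary visit without a prespecified analysis is not in itself an error, and Aims 1-3 are consistent in ending at post. The timeline does mention follow-up tests, and the study-flow figure (Figure 9) is not shown, so the visit may appear there.

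Most of this stands and keeps the point minor. It does not remove the contradictions. A correct duration does not make 9 sessions right. A flow figure could not reconcile a stated total of three evaluations with a stated total of four, nor supply an analysis.

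Some stronger readings are tempting, and the documents do not support them:
- **Candidates are told of too few hours.** Session length is 2 hours in Specific Aims, 2 to 3 hours in Dose and about 3 hours on the form. The plan also does not say which assessments share a treatment day. No shortfall in hours or net visits can be shown.
- **Participants consented to the wrong schedule.** The consent form is not in the copy reviewed.
- **The 9 sessions and the SAP's 3 weeks are remnants of a 3-week design.** The arithmetic fits (3 × 3 = 9), but nothing in the documents says so.
- **The SAP phrase cuts off the analysis period.** It is descriptive only, as shown in the working.

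**Conclusion.** The text is wrong as written, and the point is minor.

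First, item 8 gives 9 rehabilitation sessions where three protocol sections give 12, and attendance is an eligibility matter. The error is confined to the session count. That the 8-week total fits 12 sessions rests on the form's own rule of 30 days after the last session and on a last session late in week 4.

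Second, the protocol requires a 30-day evaluation in one section and omits it from the Methods assessment text, and the form's count agrees with neither. No stated analysis uses the visit. Because Figure 9 is not shown, the omission is claimed for the text only.

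The SAP's 3-week phrase is an editorial slip. A reader might infer that the main result is at risk. It is not: sample size, the main Aim 1 comparison and the Aim 3 occasions are unaffected.

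**What to change.** **If the 30-day visit is intended:**
- Questionnaire item 8: state 12 rehabilitation sessions and four evaluations including the 30-day follow-up. Keep the total at about 8 weeks, plus any lead for the pre-treatment evaluation.
- Methods: list the 30-day visit as the fourth evaluation under Evaluation Sessions, and align the kinematic and EMG time points.
- SAP: add one secondary contrast of Targeted against Non-Targeted on the Rasch FMA-UE at follow-up. Leave the main Time factor at Pre, Mid, Post.
- SAP, Missing Data: describe a 4-week treatment period and a 30-day follow-up. A bare change from three to four weeks would be wrong once the visit is kept.

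**If it is not intended:** remove it from the Project Timeline, Potential Risks and the questionnaire, and state three evaluations throughout. Still correct item 8 to 12 sessions, restate its total time without the follow-up, and change the SAP phrase to a 4-week treatment period.

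The cost is a few text corrections and at most one secondary contrast, on data that Potential Risks and the form already call for. Sample size, treatment and the main analysis do not change.
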